- described and details on how and when the subject was diagnosed are documented in the subjects source data/medical records by a current or previous physician or the PI, this is sufficient and the subject can be enrolled in the trial.
3. On stable antiretroviral therapy (ART) i.e. Combination ART for at least three months prior to screening visit in this clinical trial with no change to the therapy during these three months.
  4. Screening HIV-1 RNA < 200 copies/ml
  5. Screening CD4 counts  $\geq 100$  cells/ $\mu$ l and  $\leq 500$  cells/ $\mu$ l.
  6. Documented nadir CD4 count < 200 cells/ $\mu$ l at any time prior to screening visit. If nadir is not documented lowest documented CD4 count < 200 cells/ $\mu$ l at any time prior to screening visit.
  7. Hemoglobin  $\geq 9.0$  g/dl for female subjects,  $\geq 10.0$  g/dl for male subjects.
  8. Platelets  $\geq 100,000/\text{mm}^3$ .
  9. Ability and willingness of subject to provide written informed consent.
  10. Body Mass Index (BMI)  $\geq 18.5$  and < 35 kg/m^2.
  11. Women of childbearing potential (WOCBP) must have used an acceptable method of contraception for 30 days prior to the first vaccination, must agree to use an acceptable method of contraception during the trial, and must avoid becoming pregnant for at least 28 days after the last vaccination. A woman is considered of childbearing potential unless post-menopausal (defined as  $\geq 12$  months without a menstrual period) or surgically sterilized. Acceptable contraception methods are restricted to abstinence, barrier contraceptives, intrauterine contraceptive devices or licensed hormonal products.
  12. WOCBP must have a negative serum pregnancy test at screening (SCR) and a negative urine pregnancy test within 24 hours prior to each vaccination.
  13. Absolute neutrophil cell count  $\geq 750/\text{mm}^3$ .
  14. Adequate renal function defined as a calculated Creatinine Clearance (CrCl) > 60 ml/min as estimated by the Cockcroft-Gault equation.
    - a) For men:  $(140 - \text{age in years}) \times (\text{body weight in kg}) \div (\text{serum creatinine in mg/dl} \times 72) = \text{CrCl (ml/min)}$
    - b) For women: multiply the result for men by 0.85 = CrCl (ml/min).

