## 8.2.8 Safety Laboratory Measurements

The intensity of laboratory / systemic quantitatively measured toxicities will be graded according to the toxicity scale in [Section 16.1; Appendix I: Toxicity Scale for Laboratory Values](#). These grading scales include the laboratory values determined with the routine safety parameters. In case of other laboratory values not included in the routine safety laboratory and not listed in [Section 16.1; Appendix I: Toxicity Scale for Laboratory Values](#), the [Division of AIDS Table for Grading the Severity of Adult and Pediatric Adverse Events, Version 1.0](#), December 2004, Clarification August 2009 will be used for grading of laboratory toxicities.

Safety laboratory is determined at SCR, Visit 2, Visit 4, Visit 7 (Group 3 only) and at any other visit(s) if clinically indicated. The safety laboratory measurements are performed at a central laboratory. Laboratory normal ranges are provided by the central laboratory and filed in the Investigator File. Safety laboratory parameters to be evaluated are:

Hematology: Red blood cell count, hemoglobin, total and differential White Blood Cell count (WBC), platelet count (Hematocrit, mean corpuscular/cell volume (MCV), mean corpuscular/cellular hemoglobin (MCH) , mean corpuscular hemoglobin concentration (MCHC) and red blood cell distribution width (RDW) are routinely performed as part of the complete blood cell count and will be included in the laboratory report).

HIV specific parameters: CD4 count will be determined with every safety laboratory and at Visit 8 and FU 1 and FU 2. Viral load will be determined at SCR and at Visit 2. Viral load will be determined at any other visit if clinically indicated.

Serum chemistry:

Total bilirubin, AP, AST, ALT, serum creatinine (for calculation of CrCl at SCR), sodium, potassium, calcium, troponin I (troponin mandatory at SCR and in addition Visit 2, Visit 4 and Visit 7 (Group 3 only)).

Pregnancy test:

A  $\beta$ -human choriongonadotropin (HCG) pregnancy test will be conducted for all WOCBP at SCR, within 24 hours prior to each vaccination and at the individual last active trial phase visit (i.e. Visits 1, 3, 5 and Visits 6 and 8 for Group 3 respectively). At SCR a serum  $\beta$ -HCG pregnancy test will be performed; all other pregnancy tests will be conducted as urine  $\beta$ -HCG tests.

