#### HIV Related

- Viral Load (only at Visit SCR and Visit 2)
- CD4 count (at Visit SCR, Visit 2, Visit 4, Visit 7, Visit 8 and FU 1 and FU 2)

Pregnancy test (serum  $\beta$ -HCG pregnancy test at SCR and urine  $\beta$ -HCG pregnancy test within 24 hours prior to each vaccination and at last active trial phase visit for women of childbearing potential).

Information on all pregnancy tests will be listed.

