## **3.5 Analysis and Presentation Methods**

### **3.5.1 Listings and Descriptive Statistics**

All individual data entered in the eCRF and derived data will be listed as measured in the Individual Subject Data Listing.

For ELISA and PRNT titers descriptive statistics will be based on Geometric Means and confidence intervals (CI). Other, continuous measurements will be summarized by means of descriptive statistics (i.e. number of observations (N), mean, SD, minimum (Min), median, maximum (Max)) and categorical data will be summarized by means of frequency tables (i.e. count and percentages) and CI, if not stated otherwise.

All tables and listings will be sorted by scheduled visit (and subject, if appropriate).

All tables will be presented split by treatment groups (Groups 1 - 3).

Repeat assessments/measurements and unscheduled assessments/measurements will be included in the Individual Subject Data Listing. In case of any repeats of safety laboratory values, the repeat values will be used for the before-treatment assessment and the original value for the post-trial assessment. All other repeat values will be listed in a separate listing.

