### **3.5.10 Clinical Laboratory Variables (Hematology, Chemistry, HIV)**

All measured hematology and chemistry values (and changes from baseline for continuous parameters) will be listed and summarized per visit using descriptive statistics.

Summary tables will be produced for the number of high and low laboratory values per visit by hematology and chemistry parameters.

In addition, all clinical laboratory values outside the normal range will be listed with screening number, demographic information and flagging of abnormal values (L=Below normal range, H=Above normal range) with their clinical significance.

‘Shift tables’ will be used to evaluate categorical changes from SCR to Visit 2 and SCR to Visit 4 (and SCR to Visit 7 in Group 3) with respect to normal ranges (below, within, above normal range) in hematology and chemistry parameters.

Measured CD4 count and viral load values and changes from Baseline will be summarized per visit using descriptive statistics. A plot of median CD4 counts per visit and per treatment group will be produced. All measured values will be listed.

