### **15.3.3 Laboratory Results**

15.3.3.1 Laboratory Data (Mean Values): Hematology – FAS  
15.3.3.2 Laboratory Data (Mean Values): Biochemistry – FAS  
15.3.3.3 Laboratory Data (Mean Values): CD4 – FAS  
15.3.3.4 Laboratory Data (Mean Values): Viral Load – FAS  
15.3.3.5 Laboratory Data (Shift Table): Hematology – FAS  

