15.3.3.6 Laboratory Data (Shift Table): Biochemistry – FAS  
15.3.3.7 Laboratory Data (Shift Table): CD4 – FAS

### **15.3.4 Vital Signs and ECG Data**

15.3.4.1 Vital Signs – FAS  
15.3.4.2 ECG Data: Global Information – FAS  
15.3.4.3 ECG Data (Shift Table): Global Information – FAS  
15.3.4.4 ECG Data: Investigator Assessment – FAS

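### Entry requires HIV-1 RNA below 200 copies/ml, but the SAP gives viral load only raw-scale descriptive statistics, with no count at or above that limit, no shift table and no rule for below-limit results

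*SAP*

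**What the plan says.** Protocol 1.5, inclusion criterion 4, sets the entry limit: "Screening HIV-1 RNA < 200 copies/ml". Criterion 3 adds stable combination antiretroviral therapy for at least three months before screening.

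SAP 3.5.10 sets the analysis: "Measured CD4 count and viral load values and changes from Baseline will be summarized per visit using descriptive statistics". SAP 3.5.1 defines the descriptive statistics for continuous measurements as "number of observations (N), mean, SD, minimum (Min), median, maximum (Max". The table index in SAP 5.1 holds one viral load table, 15.3.3.4, "Laboratory Data (Mean Values): Viral Load – FAS". The same section indexes shift tables for hematology, for biochemistry and for CD4 (15.3.3.7, "Laboratory Data (Shift Table): CD4 – FAS"), but none for viral load.

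On timing, the HIV entry in SAP 3.4.2 reads "Viral Load (only at Visit SCR and Visit 2", which matches the only scheduled tests. Protocol 8.2.8 adds: "Viral load will be determined at any other visit if clinically indicated". Footnote 7 to the SAP section 2 schedule also allows clinically indicated tests during the treatment period.

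For antibody titers below the detection limit, the SAP's General Definitions assign the value 1. The SAP has no corresponding rule for viral load.

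**The concern.** Every eligible subject starts below 200 copies/ml and receives a standard or intensified vaccine regimen. The safety question is therefore categorical: how many subjects are at or above that limit afterwards, and in which group? Viral load after a rebound can be orders of magnitude above suppressed values. On the raw scale a few subjects then determine the mean and SD, while the median stays at the suppressed level until about half the group has rebounded. The planned statistics describe the size of the largest values better than the number of subjects affected.

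The missing below-limit rule matters for the change from baseline. If the laboratory reports such results as text rather than numbers, a change cannot be computed for a subject who starts below the limit, and that could include a subject who later rebounds. If a value is substituted, the SAP should say which.

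At stake is whether the study report can state, by group, the number of subjects with HIV-1 RNA of 200 or more after vaccination. The primary objective is the safety of a higher dose or more injections, in people with HIV.

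**Working it through.** **1. The plan's own figure.** The documents give no figure for viral load. The nearest safety figure is in Protocol 9.2 and SAP 3.1: with 30 subjects per group, an adverse event of incidence 1 in 10 is seen at least once with probability of at least 95%. Check: 1 − 0.9^30 = 0.9576. It reproduces. It is also a statement about subjects with an event, which is the form of summary that viral load lacks.

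**2. What raw-scale statistics show.** From the documents: n = 30 per group and the limit of 200 copies/ml. Assumed: all suppressed values equal b = 50 copies/ml (range tried 20 to 199), and rebound values of 50,000 or 5,000.

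- A: one subject at 50,000. Mean = (29b + 50,000)/30.
- B: ten subjects at 5,000. Mean = (20b + 10 × 5,000)/30.

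| | A | B |
|---|---|---|
| Mean, b = 50 | 51,450/30 = 1,715 | 51,000/30 = 1,700 |
| Mean, b = 20 to 199 | 1,686 to 1,859 | 1,680 to 1,799 |
| Median, b = 50 | 50 | 50 |
| Minimum, b = 50 | 50 | 50 |
| SD, b = 50 | 9,120 | 2,373 |
| Maximum | 50,000 | 5,000 |
| n/N ≥ 200 | 1/30 (3.3%) | 10/30 (33.3%) |

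Mean, median and minimum hardly differ or do not differ at all. SD and maximum do differ, and the maximum shows that at least one subject is above 200. None of the six statistics gives the number of subjects. If all 30 start at 50, the mean changes are 1,665 and 1,650, with median change 0 in both.

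**3. Log10 scale.** With b = 50, log10 b = 1.699.

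- A: (29 × 1.699 + 4.699)/30 = 1.799, geometric mean 62.9.
- B: (20 × 1.699 + 10 × 3.699)/30 = 2.366, geometric mean 232.1.
- C, three subjects at 500: (27 × 1.699 + 3 × 2.699)/30 = 1.799, geometric mean 62.9.

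The log scale separates A from B, but not A (1/30) from C (3/30), because one rise of three logs equals three rises of one log. It improves the continuous summary but does not replace the count.

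**4. What a count would give.** Exact (Clopper-Pearson) 95% intervals with N = 30:

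- 0/30: 0% to 11.6% (upper limit 1 − 0.025^(1/30))
- 1/30: 0.1% to 17.2%
- 3/30: 2.1% to 26.5%

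**5. What the schedule can support.** Planned vaccinations: 60 × 2 (Groups 1 and 2) + 30 × 3 (Group 3) = 210. A scheduled viral load, at Visit 2, follows only the 90 first vaccinations. The other 120 (90 second vaccinations and 30 boosters) have clinically indicated tests only. At Visit 2, Groups 1 and 3 have had identical treatment.

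**The case against.** The strongest reply is that the plan already covers viral load adequately for a variable that is not an endpoint. Change in CD4 count is the only HIV laboratory measure named as an endpoint, which may explain why CD4 has a shift table and viral load does not. Every measured viral load is listed (SAP 3.5.10, Listing 16.2.3.3.5), and a trial of 90 subjects can be read by hand. Protocol 8.1.2.1 requires any laboratory abnormality judged clinically significant to be recorded as an adverse event, so a real loss of control can reach the adverse event tables. Much of this stands and limits the weight of the point. It does not supply the count. The adverse event route depends on investigator judgement, viral load is absent from the Appendix I scales behind the automatic Grade 3/4 recording rule, and SAP 3.5.9 keeps adverse events starting more than 28 days after a vaccination out of the summary tables.

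A reader might infer more than the documents support:

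- *That viral load is summarised by means alone.* The title of Table 15.3.3.4 suggests it, but the wording is shared by Tables 15.3.3.1 to 15.3.3.4, and SAP 3.5.1 adds SD, minimum, median and maximum.
- *That the table could not tell one rebound from a rise in everybody.* It could. If all 30 rose from 50 to 382, the minimum would be 382 and the median change 332. One rebound to 10,000 gives nearly the same mean change (9,950/30 = 331.7) but a median change of 0.
- *That tests after the second dose or booster reach no table.* The restriction in SAP 3.4.2 and the assignment of unscheduled values to a listing in SAP 3.5.1 point that way. SAP 3.5.10 says per visit without naming visits, and the adverse event route exists. The texts need reconciling; they do not settle the matter.
- *That the SAP causes the lack of later data.* It follows the protocol schedule, and no SAP wording can supply tests that were not done.

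**Conclusion.** The point holds as a gap in safety presentation. The SAP gives viral load no threshold count, no shift table and no below-limit rule, although entry is defined by a threshold. In the illustration, the planned mean and median barely distinguish 1/30 from 10/30 subjects at or above 200 copies/ml. The maximum shows that a rebound occurred, but not in how many.

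The illustration rests on assumed values, because the documents give no viral load distribution, assay limit or result format. That many baseline values lie below the assay limit is plausible but not stated; only the limit of 200 is. The documents use 200 solely as an entry criterion, so counting at 200 is a reporting choice. One value at or above it should not be labelled virological failure.

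The importance is modest. No protocol commitment is breached, and every value remains visible in a listing.

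**What to change.** In SAP 3.5.10 and Table 15.3.3.4:

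1. Add, by group, the number and percentage of subjects with HIV-1 RNA of 200 copies/ml or more at Visit 2, with a Clopper-Pearson 95% CI. N is the number with a Visit 2 result.
2. Add a shift from screening to Visit 2 in two categories, below 200 and 200 or more. The upper screening row should be empty apart from eligibility deviations, so the table also separates new crossings from subjects already above the limit.
3. Report any continuous summary, including change from baseline, on the log10 scale. Set below-limit results to the assay limit and state that limit.
4. Reconcile the visit restriction in SAP 3.4.2 with the per-visit wording of SAP 3.5.10 and the clinically indicated tests allowed by Protocol 8.2.8 and SAP section 2, footnote 7. Show those later results as the number at 200 or more out of the number tested, without confidence intervals, and with a footnote that testing was indication-driven. Subjects tested because of a clinical indication are a selected sample, so such a proportion does not estimate a rate over all vaccinated subjects.

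The cost is SAP wording and one revised table. No new data are needed.

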### **3.5.11 Vital Signs and ECG**

Measured vital signs values and changes from Baseline will be summarized at each time point using descriptive statistics. All measured values will be listed.

The investigator’s overall interpretation of either normal, abnormal and if abnormal whether the ECG is clinically significant or not clinically significant, will be summarized at Screening and Visit 2. All ECGs including those clinically indicated and those not clinically indicated will be listed. In addition shift tables between SCR and Visit 2 will be produced to summarize the number of changes in ECG status.

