### ECG

A standard 12-lead ECG will be taken at the SCR and at Visit 2. At Visit 4 and Visit 7 (Group 3 only) an ECG is only done if clinically indicated. ECGs will be evaluated by a central ECG reading center. The workflow and communication flow will be provided in a separate manual.

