### **9.4.2 Presentation of Data**

For biometrical analysis, data obtained in this trial and documented in the eCRFs will be listed. For parameters of interest, summary tables with descriptive group statistics for metrical variables will be prepared. For categorical / dichotomous variables summary tables showing the absolute and relative count in each category will be prepared.

Full details of the analyses will be defined in the Statistical Analysis Plan (SAP). The SAP will be finalized prior to the respective database lock. The CRO will be responsible for data management and statistical evaluation. Data will be analyzed using SAS®.

Antibody titers and derived parameters, e.g. GMTs and seroconversion rates, will be assessed by vaccinia-specific ELISA and vaccinia-specific PRNT methods as described in [Section 7.1](#).

Clinical laboratory test results will be marked whether the result is below, within or above the respective reference range. The number of values outside of the corresponding reference range will be counted.

All ECGs will be evaluated by a centralized procedure as described in the ECG Assessment Plan. Detailed descriptive analysis of the reasons/category of ECG abnormalities will be performed.

The occurrence of solicited local and general AEs during the 8-day period post vaccination (Days 0–7) will be summarized on a per subject and per vaccination basis.

Unsolicited AEs will be coded using MedDRA coding terminology. The intensity of AEs will be graded according to [Section 8.2](#).

AESIs will be separately listed and tabulated.

SAEs will be listed separately. Each SAE will be described individually in detail.

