## **1 Trial Overview**

### **1.1 Trial Description**

This trial is a randomized, open-label Phase II trial to assess the safety and immunogenicity of MVA-BN smallpox vaccine when increasing the number of injections compared to the standard regimen in immunocompromised subjects with HIV infection.

In total, ninety (90) vaccinia-naïve Human Immunodeficiency Virus (HIV) infected subjects will be enrolled in this trial. All subjects will be randomly assigned (1:1:1) to one of three groups (Groups 1-3) to receive:

Group 1:

One injection at Day 0 and Day 28 with 0.5 mL Modified Vaccinia Ankara Strain – Bavarian Nordic (MVA-BN) smallpox vaccine containing at least  $1 \times 10^8$  Tissue Culture Infectious Dose 50% (TCID50) per mL (standard regimen)

Group 2:

Two injections at Day 0 and two injections at Day 28 with 0.5 mL MVA-BN smallpox vaccine each containing at least  $1 \times 10^8$  TCID50 per mL (double dose regimen)

Group 3:

One injection at Day 0 and Day 28 with 0.5 mL MVA-BN smallpox vaccine containing at least  $1 \times 10^8$  TCID50 per mL (standard regimen) and one booster injection at Day 84 (Week 12) with 0.5 mL MVA-BN smallpox vaccine containing at least  $1 \times 10^8$  TCID50 per mL (booster regimen)

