#### 12-lead Electrocardiogram (ECG) (at SCR and Visit 2)

(Additional ECGs will be performed and reported if clinically indicated [e.g. Visit 4 or Visit 7], or in case of any clinically significant cardiac events are present)

- Investigator's overall interpretation (normal, abnormal)
- Clinical significance

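### The SAP describes an ECG summary of the investigator's call only and omits the abnormality-category analysis promised in the protocol; the role of the central reading in the tables is undefined

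*SAP*

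**What the plan says.** **Protocol.** The ECG part of section 8.2.7 states that "ECGs will be evaluated by a central ECG reading center". Section 9.4.2, which covers how data are to be presented, repeats this and adds an analysis: "All ECGs will be evaluated by a centralized procedure as described in the ECG Assessment Plan", followed by "Detailed descriptive analysis of the reasons/category of ECG abnormalities will be performed". The same section leaves the full analysis details to the SAP.

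**SAP text.** Section 3.4.2 lists two ECG variables: the investigator's normal/abnormal interpretation, and clinical significance. Section 3.5.11 takes the investigator's interpretation and, for abnormal tracings, "whether the ECG is clinically significant or not clinically significant, will be summarized at Screening and Visit 2". It also lists all ECGs and states that "shift tables between SCR and Visit 2 will be produced to summarize the number of changes in ECG status". No reader is named for that shift table. Section 3.6 gives the alterations from the protocol as none.

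**SAP index.** Table 15.3.4.2 is "ECG Data: Global Information – FAS". Table 15.3.4.3 is the corresponding shift table. Table 15.3.4.4 is a separate Investigator Assessment table. The central reading is named once, in the title of listing 16.2.3.4.2.

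**The concern.** Safety is the primary objective, and the protocol singles out cardiac monitoring as a precaution for this vaccine class (section 8). Clinically significant ECG changes are one criterion for an adverse event of special interest (AESI, section 8.1.2.3). The protocol therefore plans two safeguards for the ECG data: a central reading and a breakdown by type of abnormality. The SAP methods text carries neither forward.

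Two things are at stake. First, a normal/abnormal split cannot show what kind of abnormality appeared. The protocol itself treats kinds differently: its appendix on screening ECGs separates non-specific ST and T wave changes from complete bundle branch block. Second, "This trial is a randomized, open-label Phase II trial", so an investigator judging the post-vaccination tracing can know whether the subject received one injection or two.

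The SAP also says that it will be followed in full and that unforeseen additional analyses will be flagged as unplanned. A category table added at reporting could then carry that label although the protocol promised it.

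**Working it through.** No statistic of the plan is involved, so the check sets the documents side by side and counts the recordings concerned.

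| Element | Protocol | SAP methods text (3.4.2, 3.5.11) | SAP index |
|---|---|---|---|
| Central reading | All ECGs (8.2.7, 9.4.2) | Not mentioned | Named in listing 16.2.3.4.2 only |
| Abnormality reason or category | Descriptive analysis (9.4.2) | Not mentioned | In no table title |
| Investigator's call | Investigator assesses significance of cardiac events (8.2.7) | Defined and summarised | Table 15.3.4.4 |
| Shift from Screening to Visit 2 | Not specified | Reader not named | Table 15.3.4.3, content undefined |
| Declared departure | Not applicable | 3.6: none | Not applicable |

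1. The category analysis is absent from both the SAP text and the table titles. This holds however the Global Information tables are read.
2. The central reading is absent from the methods text. Whether it is tabulated depends on tables 15.3.4.2 and 15.3.4.3, whose titles name no variable, reader or category.
3. The investigator's call is the only ECG summary that the SAP describes.

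**Recordings concerned.** Planned enrolment is 90, with scheduled ECGs at Screening and Visit 2. Those at Visits 4 and 7 are taken only if clinically indicated.

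- Scheduled ECGs with full attendance: 90 × 2 = 180.
- Scheduled after vaccination: 90 × 1 = 90, all at Visit 2.
- Of these, 30 are from Group 2 after two injections, and 30 + 30 = 60 are from Groups 1 and 3 after one injection each.

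Randomization takes place at Visit 1, after the Screening ECG, so the regimen cannot be known when that ECG is taken. Only the Visit 2 half of each shift is exposed to an open-label judgement, and the regimens that differ at that point are Group 2 against Groups 1 and 3. Visit 2 is also the only scheduled post-vaccination ECG, so no later scheduled tracing supplements it.

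**The case against.** The strongest reply is that the index is part of the SAP. It lists the two Global Information tables apart from the Investigator Assessment table, which suggests that they hold something other than the investigator's call, possibly the central reading, and SAP 3.5.1 splits all tables by group. This stands as far as it goes. A reader might infer that central results will go untabulated, or that every shift table rests on the investigator; the documents support neither. They show that the content of these tables is undefined. A title is not a specification, and no title offers categories.

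A second reply is that summarising the investigator's call is legitimate, because clinical significance is what makes an ECG change an AESI. That is correct, and the table should stay. Significant changes also reach the AESI table by preferred term, or the serious adverse event analysis if they are serious, which gives some breakdown by type. It does not cover abnormalities judged not significant.

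Third, the ECG Assessment Plan and the ECG workflow manual are not among the documents. They may define categories, or give the investigator the central report before the call is made, which would narrow the contrast between readers. That is possible, but the protocol assigns full analysis details to the SAP.

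Finally, ECG results are not a separately named endpoint, all ECG outputs are descriptive, and the listing places both readings side by side. This limits the seriousness of the gap. A listing is still not a descriptive analysis by group.

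**Conclusion.** The point holds in limited form. The SAP omits the protocol's analysis by reason or category of ECG abnormality, describes only an investigator-based summary, leaves the reader and content of tables 15.3.4.2 and 15.3.4.3 undefined, and declares no departure. It should be corrected, but it does not threaten the trial's main conclusions.

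The missing category analysis is certain on the text. The open-label concern is narrower: it applies to about 90 Visit 2 ECGs, assuming full enrolment and attendance, and the size or direction of any reader effect cannot be derived. It would be tempting to treat the central reading as blinded and therefore free of this problem. The protocol states blinding for the immunogenicity laboratory staff but says nothing either way about the ECG readers. The case for tabulating the central reading rests on the protocol's own commitment, not on assumed blinding.

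**What to change.** - In SAP 3.4.2, add the central reading as an ECG analysis variable: normal/abnormal plus abnormality category, with the categories taken from the ECG Assessment Plan or listed in the SAP.
- In SAP 3.5.11, tabulate that variable by group at Screening and Visit 2. State that the central reading feeds table 15.3.4.2 and the Screening to Visit 2 shift table 15.3.4.3, and retitle both to say so.
- Keep the investigator's clinical-significance call as its own table, 15.3.4.4, because it feeds the AESI definition.
- State whether the central readers know the group assignment.
- If the sponsor prefers not to produce the category analysis, record that departure and its reason in SAP 3.6.

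The cost is SAP wording and one or two descriptive tables. The protocol already requires central evaluation of all ECGs, so no new data are needed.
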